2.3. Safety Endpoints

Safety variables to be assessed include: adverse events, clinical laboratory tests (hematology, clinical chemistry, and urinalysis), vital sign measurements (systolic and diastolic blood pressures, respiration rate, heart rate, and oral or ear body temperature), physical exam, and electrocardiograms.

2.4. Other Assessments

- Hair quality assessment including normalization of exclamation point hairs and hair shedding will be described.
- Vellus and Indeterminate scalp hair will be described.
- Non-scalp hair assessments (body and nasal hair) will be described.

Date: 09NOV2018, Version 1.0 Page 22 of 80 CONFIDENTAL

3. INVESTIGATIONAL PLAN

3.1. Overall Study Design

Protocol: ATI-502-AA-203

This Phase 2, multicenter, open-label study will evaluate the safety, efficacy, and durability of efficacy of ATI-502 Topical Solution, 0.46% for the treatment of alopecia areata (AA), alopecia universalis (AU) and alopecia totalis (AT) in adult subjects who completed 24 weeks of treatment with ATI-501 Oral Suspension or Placebo Suspension.

Subjects who complete 24 weeks of active treatment with ATI-501 Oral Suspension or Placebo Suspension in study ATI-501-AUAT-201 will be assessed for eligibility to enter the study. At Visit 9 in study ATI-501-AUAT-201, subjects who did not experience any adverse events (AEs), serious adverse events (SAEs), or tolerability issues that met study discontinuation criteria in study ATI-501-AUAT-201 and who in the opinion of the investigator are capable of regrowing scalp hair or maintaining prior regrowth experienced in ATI-501-AUAT-201 and meet the other entry criteria are eligible to enroll in this open-label study.

Enrolled subjects will apply ATI-502 Topical Solution, 0.46% BID to the entire scalp and if applicable, the eyebrow(s) and return for safety and efficacy assessments as detailed in the Schedule of Assessments (Table 3). Assessment of response to treatment and durability of response will be performed at Week 4, Week 8, Week 16, Week 24, and post-treatment Week 28. Safety and tolerability will be evaluated at each study visit by assessment of adverse events, clinical laboratory tests, and vital signs, and at Week 24, and physical examination findings.

3.2. Number of Subjects

Approximately 80 subjects will be enrolled at approximately 25 US sites.

3.3. Treatment Assignment

Subjects will apply ATI-502 Topical Solution, 0.46% twice-daily for 24 weeks followed by a 4-week post-treatment follow up period.

3.4. Dose Adjustment Criteria

Subjects should not modify the study medication dosage or frequency without the investigator's prior approval. All study medication modifications must be reported on the appropriate eCRF. If study medication intolerance or safety issue occurs, after consulting with the Aclaris Therapeutics, Inc. Medical Monitor (see page 1), the investigator or designee may direct the subject to modify the study medication frequency from twice-daily to once-a-day. If the subject cannot apply the study medication twice-daily for more than 4 consecutive days, other dose modifications and continuation in the study must be reviewed with the Medical Monitor.

Date: 09NOV2018, Version 1.0 Page 23 of 80 CONFIDENTAL

3.4.1. Safety Criteria for Adjustment or Stopping Doses

3.4.1.1. Study Medication Interruption

Protocol: ATI-502-AA-203

Treatment with ATI-502 Topical Solution should be temporarily interrupted in the event of severe adverse events considered related to ATI-502, or in the event of one or more of the abnormal laboratory values listed in Table 2.

Table 2: Study Medication Interruption Criteria

Laboratory Test	Hold Study Medication if:	Resume Study Medication if:
WBC count	$< 2 \times 10^{3}/\mu L$	$\geq 2.5 \times 10^{3}/\mu L$
ANC	$< 1 \times 10^{3}/\mu L$	$\geq 1.5 \times 10^{3}/\mu L$
Lymphocyte count	$< 0.5 \times 10^{3}/\mu L$	$\geq 0.75 \times 10^{3}/\mu L$
Platelet count	$< 75 \times 10^3 / \mu L$	Returns to Baseline values
Hemoglobin	< 8 g/dL or a decrease > 2g/dL (from baseline value on ATI- 501-AUAT-201)	$\geq 10 \text{ g/dL}$
AST or ALT	> 3 x ULN	< 2 x ULN or within 20% of Baseline values
Serum creatinine	>2 x ULN	<1.5 x ULN or within 10% of Baseline value

Subjects with one or more of laboratory values meeting the Study Medication Interruption Criteria found in Table 2 must have repeat lab testing performed with results meeting the minimum criteria for resumption in order to initiate treatment

During treatment, if a subject has one or more of the abnormal laboratory values noted in Table 2, the investigator or designee upon receipt and review of the central laboratory report should instruct the subject to hold study medication dosing. The investigator or designee should ask the subject about symptoms, concomitant illnesses and medications and repeat the test(s) as soon as possible. The Medical Monitor must be notified of dose interruptions due to SAEs considered related to study medication or laboratory abnormalities noted in Table 2.

If the retest confirms the abnormal laboratory value, then the study medication should continue to be held followed by repeat testing once a week or sooner at the discretion of the investigator. The subject should be followed until the laboratory abnormality(s) returns to normal or to Baseline (Visit 1) values.

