I will maintain adequate source documents and record all observations, treatments and procedures pertinent to trial subjects in their medical records. I will accurately complete the case report forms supplied by the Sponsor in a timely manner. I will ensure that my facilities and records will be available for inspection by representatives of the Sponsor, the IRB, and/or local regulatory authorities. I will ensure that I and my staff are available to meet with Sponsor representatives during regularly scheduled monitoring visits.

I will notify the Sponsor within 24 hours of any serious adverse events. Following this
notification, an initial written report describing the serious adverse event will be provided to the
Sponsor within 24 hours of Investigator awareness of the event.

	_
Printed Name of Investigator	
Signature of Investigator	Date

Date: 09NOV2018, Version 1.0 Page 3 of 80

Phase of development: 2

SYNOPSIS

Protocol: ATI-502-AA-203

Name of Sponsor/Company: Aclaris Therapeutics, Inc.

Name of Investigational Product: ATI-502 Topical Solution

Name of Active Ingredient: ATI-502

Title of Study: Open-Label Study of ATI-502 Topical Solution for the Treatment of

Alopecia Areata (AA), Alopecia Universalis (AU) and Alopecia Totalis (AT)

Study center(s): Approximately 25 US study centers

Studied period (years):

Estimated date first patient enrolled: December 2018 Estimated date last patient completed: January 2020

Objectives:

To assess the safety, tolerability, and efficacy of ATI-502 Topical Solution in subjects with AA, AU or AT following 24 weeks of treatment with ATI-501 Oral Suspension or Placebo Suspension.

To assess the ability of ATI-502 Topical Solution to maintain or improve hair regrowth in subjects previously treated with ATI-501 Oral Suspension or Placebo Suspension.

Methodology:

This Phase 2, multicenter, open-label study will evaluate the safety, tolerability, efficacy, and durability of efficacy of ATI-502 Topical Solution, 0.46% for the treatment of alopecia areata (AA), alopecia universalis (AU) and alopecia totalis (AT) in adult subjects who completed 24 weeks of treatment with ATI-501 Oral Suspension or Placebo Suspension.

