3.4.1.2. Study Medication Discontinuation

Study medication should be permanently discontinued in the event of any of the following:

- Severe infection requiring parenteral antimicrobial therapy or hospitalization
- Symptomatic herpes zoster
- Malignancy
- Anaphylactic or severe allergic reaction

Date: 09NOV2018, Version 1.0 Page 24 of 80 CONFIDENTAL

• WBC Count: $< 1 \times 10^3/\mu$ L or second occurrence of $< 2 \times 10^3/\mu$ L

- ANC: $< 0.5 \times 10^3/\mu L$ or second occurrence of $< 1 \times 10^3/\mu L$
- Lymphocyte count: $< 0.3 \times 10^3/L$ or second occurrence of $< 0.5 \times 10^3/\mu L$
- Platelet count: $< 50 \times 10^3/\mu L$ or second event of $< 75 \times 10^3/\mu L$ in each case, value should be confirmed by retesting before treatment discontinuation
- Hemoglobin: < 6.5 g/dL or second occurrence of < 8 g/dL in each case, value should be confirmed by retesting before treatment discontinuation
- AST or ALT:

Protocol: ATI-502-AA-203

- > 5 x ULN persisting for 2-weeks of study medication interruption or second event of > 5 x ULN
- > 3 x ULN with total bilirubin >2 x ULN or symptoms of hepatocellular injury [fatigue, nausea, vomiting, right upper quadrant pain or tenderness, fever, rash and/ or eosinophilia (>5%)].
- Serum creatinine: > 2 x ULN persisting for >2 weeks of treatment discontinuation or second occurrence of > 2 x ULN

The continued treatment of subjects who experience other serious or severe adverse events considered related to study treatment should be discussed with the Sponsor's medical monitor.

Site staff must perform protocol-required procedures for trial discontinuation and follow-up.

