8.2.1.2. Serious Adverse Event (SAE)

A serious adverse event is an AE occurring during any study phase (i.e., Baseline, Treatment, Washout, or Follow-up), and at any dose of the investigational product, comparator or placebo, that fulfills one or more of the following:

- Results in death
- It is immediately life-threatening
- It requires in-patient hospitalization or prolongation of existing hospitalization
- It results in persistent or significant disability or incapacity
- Results in a congenital abnormality or birth defect
- It is an important medical event that may jeopardize the patient or may require medical intervention to prevent one of the outcomes listed above.

The term "life threatening" refers to an event in which the subject was at risk of death at the time of event; it does not refer to an event that hypothetically might have caused death if it were more severe.

Important medical events are those that may not be immediately life threatening, result in death or hospitalization, but are clearly of major clinical significance and may jeopardize the subject or require intervention to prevent one of the outcomes listed in the SAE definition above. These should also usually be considered serious.

All SAEs that occur from the time of informed consent until 30 days following the cessation of study medication dosing, whether or not they are related to the study, must be recorded on the SAE forms provided by Aclaris Therapeutics, Inc.

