8.3.2. Severity

The investigator is to define the severity of each AE using the following definitions as a guideline. The investigator will consider the range of the possible severity of the event and identify the severity that is the most appropriate according to her/his medical judgment.

Mild – Awareness of signs or symptom, but easily tolerated

Moderate – Discomfort, enough to cause interference with usual activity

Severe – Incapacitating with inability to perform usual activity

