8.3.5. Procedure for reporting a serious adverse event

Upon becoming aware of a SAE occurring during the SAE reporting period, whether or not related to the study medications, the investigator must:

1. Take the appropriate medical action to ensure the subject's safety.

Date: 09NOV2018, Version 1.0 Page 50 of 80 CONFIDENTAL

2. Immediately inform the Safety Monitor of the SAE by email, ensuring that the subject information is deidentified (only subject initials and subject number) to: **ProPharma**,

Email: [contact].

- 3. Print a copy of the email confirmation from ProPharma and place in the study file.
- 4. Within 24-hours complete, as fully as possible, an AE eCRF and an SAE form; e-mail the forms and any other relevant information (*e.g.*, concomitant medication eCRF, medical history eCRF, laboratory test results) to ProPharma (Aclaris Therapeutics, Inc. Safety Monitor).
- 5. Monitor and document the progress of the SAE until it resolves or, if not resolved after the subject's last study visit, until in the opinion of the investigator the SAE reaches a clinically stable outcome with or without sequelae AND the investigator and Aclaris Therapeutics, Inc. Safety and Medical Monitor agree that the SAE is satisfactorily resolved.
- 6. Inform the Aclaris Therapeutics, Inc. Safety Monitor of SAE updates, via telephone, followed by an SAE form update sent by e-mail.
- 7. Comply with the appropriate regulatory requirements and Aclaris Therapeutics, Inc. instructions regarding reporting of the SAE to the responsible Institutional Review Board (IRB) or Ethics Committee (EC).

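### Section 3.4.1.1 holds drug for related severe AEs but notifies for related serious ones, so a related AE that is serious but not severe has no stated interim hold

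*Combined protocol and SAP*

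**What the plan says.** Section 3.4.1.1 gives two triggers for a temporary hold. One is clinical: treatment "should be temporarily interrupted in the event of severe adverse events considered related to ATI-502". The other is any laboratory value in Table 2. Later in the section comes the notification duty: "The Medical Monitor must be notified of dose interruptions due to SAEs considered related to study medication or laboratory abnormalities noted in Table 2".

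Section 3.4.1.2 lists events that require permanent discontinuation. For events not on the list, it closes by sending the case to the sponsor's medical monitor: "The continued treatment of subjects who experience other serious or severe adverse events considered related to study treatment should be discussed".

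The two terms are defined in Section 8. Section 8.3.2 grades severity, with severe meaning "Incapacitating with inability to perform usual activity". Section 8.2.1.2 defines a serious event by outcome or importance. One of its criteria reads: "It is an important medical event that may jeopardize the patient or may require medical intervention to prevent one of the outcomes listed above". Table 1 expands SAE as serious adverse event, so the abbreviation cannot be read as severe.

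**The concern.** A stopping rule should tell an investigator, from the text alone, whether the subject applies the next dose. Here the hold depends on intensity and the notification on seriousness. An event can meet one test without the other: a drug-related hospitalization graded moderate is serious but not severe.

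At stake is dosing in the interval between such an event and the medical monitor discussion. Subjects apply the drug themselves twice daily, and the study runs at approximately 25 sites. If the rule is silent, each investigator decides whether to pause, and sites may decide differently. The literal reading is also oddly ordered: an isolated white cell count below 2 x 10^3/µL requires a hold, while a related hospitalization of moderate intensity does not.

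**Working it through.** No arithmetic applies. The protocol states no figure on this point and gives no rate for the events concerned. The check is to take each type of related event through every rule that could govern it.

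| Related event | Hold stated (3.4.1.1)? | Within the 3.4.1.1 notification sentence? | Other provisions |
|---|---|---|---|
| Severe and serious | Yes | Yes | Discussion under 3.4.1.2; SAE reporting under 8.3.5 |
| Serious, not severe, not on the 3.4.1.2 list, no Table 2 value | **No** | Only if dosing is in fact interrupted | Discussion under 3.4.1.2; SAE reporting under 8.3.5 |
| Severe, not serious | Yes | **No** | Discussion under 3.4.1.2 |
| Any event with a Table 2 value | Yes | Yes | Table 2 restart criteria |
| On the 3.4.1.2 list (e.g. malignancy, symptomatic herpes zoster) | Superseded | Superseded | Permanent discontinuation |

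The second row is the gap. Each provision that might close it was checked:

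1. **Section 3.4.1.2, closing provision.** It covers related serious events by name, but it asks for a discussion. It states neither a hold while the discussion is pending nor a time by which it must happen.
2. **Section 8.3.5.** Step 1 begins "Take the appropriate medical action to ensure" the subject's safety and names no drug action. Step 2 requires an immediate email to the Safety Monitor; the 24 hours in step 4 is the limit for completing the forms. These are reporting duties, and the email goes to the Safety Monitor, whereas 3.4.1.2 calls for discussion with the medical monitor.
3. **Investigator's Agreement.** "I will notify the Sponsor within 24 hours of any serious adverse events" sets a reporting limit and gives no dosing rule.
4. **Section 3.4.** A reduction to once daily is allowed after consulting the Medical Monitor, and review is required if twice-daily dosing is not possible for more than 4 consecutive days. The first is optional and is not a hold; the second applies only once dosing has already been disrupted.
5. **Section 4.3.** The investigator may remove a subject whose continuation is not in the subject's best interest. This is discretionary.
6. **The notification sentence itself.** It presupposes that related SAEs interrupt dosing but does not order it. If dosing continues, the sentence is not triggered.

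None of these orders an interim hold. The third row is the reverse gap: the drug is held, but the Section 3.4.1.1 duty to notify does not reach that hold.

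On restarting, the Table 2 column headed "Resume Study Medication if" gives laboratory criteria only. Section 3.4.1.1 states no restart condition for a hold triggered by an adverse event.

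**The case against.** The best reply is that these events are already well covered. Section 3.4.1.2 names related serious events and sends them to the medical monitor. The Safety Monitor is told immediately. The required medical action is broad enough to include stopping the drug, and Sections 3.4 and 4.3 give the investigator further room. The notification sentence shows that the authors expected related SAEs to interrupt dosing, so most investigators would probably hold anyway. The remaining set is small, because an event must be related, serious, not severe, off the discontinuation list and without a Table 2 value. Section 1.4 reports only two SAEs as of July 2018, both unrelated, in a programme where 141 subjects had applied ATI-502 or placebo.

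All of this stands as a limit on the size of the problem. It does not supply the missing rule: every provision cited is a report, a discussion without a time limit, or a discretion.

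A reader might infer that related SAEs go unmanaged in this trial, or that subjects may continue dosing for a full day before anyone is told. The documents do not support either reading, given the immediate email, the required medical action and the medical monitor discussion. Nor do they suggest that the sponsor meant to keep dosing through related SAEs. The pairing of serious with severe in Section 3.4.1.2 points to a drafting slip in Section 3.4.1.1.

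**Conclusion.** The inconsistency is real and narrow. Section 3.4.1.1 states no hold for a related AE that is serious but not severe, is off the Section 3.4.1.2 list and meets no Table 2 value. The exposure at issue runs from the event to the medical monitor discussion, for which no time is given. Separately, the section's notification sentence misses holds for related events that are severe but not serious, although Section 3.4.1.2 still sends those events to discussion.

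The size cannot be quantified from the documents. The Section 1.4 experience suggests such events will be rare, but its 141 subjects include some on placebo, so it gives no usable rate for ATI-502. The conclusion rests on reading severe and serious as the protocol defines them. This is a minor correction to a safety rule. It is worth making because the rule governs dosing, and it has no effect on any endpoint or analysis.

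**What to change.** In the hold sentence of Section 3.4.1.1, replace *severe* with *serious or severe*, keeping the limit to events related to ATI-502. This is the essential change and closes the main gap by itself.

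Use the same pairing in the notification sentence, so that every hold triggered by an adverse event is notified. Both sentences then match Section 3.4.1.2.

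If a release rule is wanted, add: *For holds triggered by an adverse event, dosing resumes only after the investigator and the medical monitor have discussed the event under Section 3.4.1.2 and agreed that restarting is acceptable.* Agreement should be the condition; otherwise the drug could restart simply because a call had taken place. Laboratory holds keep their Table 2 criteria.

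The cost is two phrase changes and one optional sentence, with no new visits, procedures or data. The downside is an occasional brief hold after a related SAE that is not severe.

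### Table 2, hemoglobin row: when the parent-study baseline is above 12 g/dL, one value can meet both the hold and the resume criterion

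*Combined protocol and SAP*

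**What the plan says.** All the governing text is in Section 3.4.1.1 (Study Medication Interruption) and its Table 2.

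- **Hold, hemoglobin:** "< 8 g/dL or a decrease > 2g/dL (from baseline value on ATI- 501-AUAT-201". There are two limbs: an absolute floor, and a fall from the baseline of the parent study.
- **Resume, hemoglobin:** at or above 10 g/dL. This is an absolute value with no baseline term.
- **Before the first dose:** subjects whose values meet a Table 2 hold criterion "must have repeat lab testing performed with results meeting the minimum criteria for resumption in order to initiate treatment".
- **On treatment:** the hold instruction opens "During treatment, if a subject has one or more of the abnormal laboratory values noted in Table 2". The retest rule follows: "If the retest confirms the abnormal laboratory value, then the study medication should continue to be held", with further testing weekly or sooner.
- **Follow-up:** "The subject should be followed until the laboratory abnormality(s) returns to normal or to Baseline (Visit 1) values". This is a different baseline from the one in the hold cell.

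Section 3.4.1.2 (Study Medication Discontinuation) uses absolute hemoglobin limits only: "Hemoglobin: < 6.5 g/dL or second occurrence of < 8 g/dL". Section 8.1.5 (Clinical Laboratory Assessments) repeats the requirement for a repeat test that meets the resumption criteria and adds nothing on this point.

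**The concern.** The hold cell has an absolute limb and a relative limb, but the resume cell is purely absolute. A subject held because of a fall from baseline may still have a hemoglobin above 10 g/dL, and so meets the resume condition at the moment the hold is triggered.

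This rule decides whether a subject is dosed after a laboratory safety signal, at approximately 25 sites (Section 3.2). If one value satisfies both columns, two sites can act in opposite ways on the same result and each be following the protocol.

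**Working it through.** **Inputs.** B is hemoglobin at the ATI-501-AUAT-201 baseline and Hb is the current value, both in g/dL. The two cells are those of the Table 2 hemoglobin row.

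- Hold: Hb < 8, or B − Hb > 2 (equivalently Hb < B − 2)
- Resume: Hb ≥ 10

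**Step 1, intersection.** The limb Hb < 8 cannot coexist with Hb ≥ 10. The limb Hb < B − 2 can. Both cells are met when

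10 ≤ Hb < B − 2,

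which contains values only if B − 2 > 10, that is, B > 12.

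**Step 2, numbers.** The baselines are illustrative, and Hb is taken in steps of 0.1 g/dL.

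| Parent baseline B | B − 2 | Values meeting both cells |
|---|---|---|
| 11.0 | 9.0 | none |
| 12.0 | 10.0 | none |
| 12.1 | 10.1 | 10.0 only |
| 13.0 | 11.0 | 10.0 to 10.9 |
| 14.0 | 12.0 | 10.0 to 11.9 |
| 15.0 | 13.0 | 10.0 to 12.9 |
| 16.0 | 14.0 | 10.0 to 13.9 |

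The limit of 12 is exact. At B = 12.0, a fall of more than 2 requires Hb below 10, which fails the resume cell.

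**Step 3, a retest on treatment.** Take B = 14.0 and a retest of 11.0. The fall is 14.0 − 11.0 = 3.0 > 2, so the abnormality is confirmed and the retest sentence keeps the subject off medication. Also 11.0 ≥ 10, so the resume cell is met.

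**Step 4, before the first dose.** Assume B = 14.0 and a Visit 1 value of 11.5. The fall is 14.0 − 11.5 = 2.5 > 2, which meets the hold cell. An unchanged repeat of 11.5 meets the resumption criterion, so treatment may start. The same 11.5 at Week 4, the first on-treatment laboratory visit in Table 3, is again a hold value.

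**Step 5, two baselines.** If that subject is later held at a lower value and returns to 11.5, the Visit 1 baseline has been reached and the resume cell is met. The value is still 2.5 below the parent baseline, so the hold cell is met too. Only at 12.0, where the fall is exactly 2.0, does the hold cell cease to apply.

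**Step 6, search for a tie-break.** The discontinuation list in Section 3.4.1.2 does not mention the fall limb. Section 8.1.5 only points back to the resumption criteria. The follow-up sentence governs how long the subject is followed and is not written as a resume condition.

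**Step 7, comparison rows.** For WBC (hold below 2, resume from 2.5), ANC (1 and 1.5) and lymphocytes (0.5 and 0.75, all ×10³/µL), a gap separates the two limits, so no value can meet both.

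**The case against.** The strongest reply is that the columns are sequential: the resume column is read only after a hold, and continuing to hold simply means holding until the resume column is met. Two other rows may support this. AST/ALT may resume within 20% of baseline, which can exceed the hold limit of 3 × ULN if baseline is above 3/1.2 = 2.5 × ULN. Creatinine may resume within 10% of baseline, which can exceed 2 × ULN if baseline is above 2/1.1 ≈ 1.82 × ULN. Overlap might therefore be intended, with the resume column governing.

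That reading is possible, but the protocol does not state it. The retest is precisely the value consulted after a hold, and in the overlap the text and the table give opposite answers for it. The AST/ALT and creatinine rows show that hemoglobin may not be the only row affected; they do not settle which instruction governs.

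A second reply is that, before the first dose, the resumption criterion is the only rule written, so nothing conflicts there. It is fair that the on-treatment instructions do not reach that stage. The result is still that a subject may start at a value for which the same table calls for interruption once treatment has begun. Inclusion criterion 7 (good general health, no unacceptable risk in the investigator's opinion) leaves room for judgment but sets no hemoglobin rule.

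Third, there are safeguards. "The Medical Monitor must be notified of dose interruptions" covers holds for Table 2 abnormalities of any length. Section 3.4 adds review of continuation: "If the subject cannot apply the study medication twice-daily for more than 4 consecutive days". Both reduce the risk. Neither says which rule prevails, and the second does not reach holds of 4 days or less.

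It also stands that every overlapping value is at least 10 g/dL, that the absolute hold and discontinuation limits are unaffected, and that no endpoint or analysis depends on this row.

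**Conclusion.** The inconsistency is real and follows from Table 2 and the retest sentence alone. The overlap is 10 ≤ Hb < B − 2. It is absent at parent baselines of 12 g/dL or below and widens by 1 g/dL for each 1 g/dL of baseline above that. The algebra needs no assumption; the baselines and the Visit 1 value used above are illustrative. How often the overlap would occur cannot be estimated, because the documents give neither a hemoglobin distribution nor a frequency of falls greater than 2 g/dL. The point should be fixed because it is a subject-safety decision rule. The Medical Monitor's involvement makes it less urgent but does not resolve it.

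**What to change.** The sponsor's medical team should reconcile four items in Section 3.4.1.1: the hemoglobin hold cell, the hemoglobin resume cell, the retest sentence and the follow-up sentence. The revised text should:

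- ensure that one value cannot satisfy both hold and resume;
- name the baseline that each item uses, parent study or Visit 1;
- state what applies before the first dose.

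Section 8.1.5 should then follow the reconciled criteria. The AST/ALT and creatinine rows can be checked for the same ambiguity at the same time. The choice of limits is clinical, and none is proposed here.

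The cost is a short protocol clarification or amendment and a memo to sites, with no new data or procedures.
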